# 9.1. Screening

Subjects with either preexisting disease recurrence or upon initial identification of clinical and pathologic recurrence of disease will be invited to enter screening. Subjects will be screened to confirm that the subject selection criteria for the study have been met. Informed consent will be obtained at screening prior to the conduct of any study-related procedures.

A screen failure is defined as a subject who has provided written informed consent, failed to meet at least one of the inclusion criteria and/or met at least one of the exclusion criteria, and not been randomized or administered investigational product(s).

A subject should not have a Visit 2 unless they meet the study criteria.

For all subjects, the plan for post-transplant immunosuppression for the duration of the study should be documented prior to randomization. Any deviation during the study from the prespecified plan should be documented with a justification for the change.

## 9.1.1. Rescreening

Individuals who consent to participate in the study but who do not initially meet all the requirements as outlined in the inclusion and exclusion criteria are not able to be enrolled; however, these individuals may be held in the screening period at the discretion of the investigator until such time that they are able to be enrolled. In this case, additional screening visits and/or repeat screening assessments may be conducted, as needed, to establish eligibility.

In the event that rescreening occurs, and the subject has not remained in the screening period, the individual is required to reconsent and must be assigned a new identification number.

# 9.1.2. Screening Procedures

## 9.1.2.1. Visit 1

The following assessments will be performed and information collected during Visit 1:

- Informed consent reviewed and signed, both for the study and for the biopsies
- Demographics
- Medical history
- Review of inclusion/exclusion criteria
- Review of concomitant medications
- Physical examination, full
- 12-lead ECG
- Dispense 24-hour urine collection container
- Dispense 3 urine protein-to-creatinine ratio (uPCR) containers for consecutive collection
- Arrange home uPCR courier pickup
- Urinalysis assessment

- Blood samples for laboratory assessments
- eGFR
- AE collection

## 9.1.2.2. Visit 2

The following assessments will be performed and information collected during Visit 2:

- Review of inclusion/exclusion criteria
- Vaccination
- Review of concomitant medications
- · Physical examination, brief
- Collect 3 uPCR containers from previous visit
- Dispense 3 uPCR containers for consecutive collection
- Arrange home uPCR courier pickup
- Urinalysis assessment
- · Blood samples for laboratory assessments
- eGFR
- Urine pregnancy test, if applicable
- AE collection
- Post-transplant immunosuppression plan for the duration of the study should be documented (prior to randomization)
- Renal biopsy (see Section 9.1.3 below for further details)

## 9.1.3. Renal Biopsy

The screening renal allograft biopsy should be conducted during the screening period and must occur within 4 weeks leading up to the day of randomization. However, a nonstudy biopsy may be used as the screening biopsy provided it meets all the following criteria:

- it was performed no more than 12 weeks prior to Week 1
- the subject has remained clinically stable since the biopsy with no changes in medication regimens that would be expected to significantly alter the screening renal allograft biopsy findings
- the prior biopsy is available for central pathology review and includes all the required components of a study screening renal allograft biopsy

## 9.1.4. Vaccinations

Subjects will be required to be vaccinated as follows on the basis of Advisory Committee on Immunization Practices (ACIP) recommendations for adults with complement deficiencies

and/or immunocompromising conditions (available at https://www.cdc.gov/vaccines/schedules/hcp/imz/adult-conditions.html).

- N. meningitidis types A, C, W, and Y: First dose at least 2 weeks prior to start of pegcetacoplan with second dose 2 months later, and then boosters every 5 years.
- N. meningitidis type B: First dose at least 2 weeks prior to start of pegcetacoplan with a second dose after at least 1 month. First booster dose 1 year later, and then additional booster doses every 2 to 3 years.
- S. pneumoniae: PCV13 and/or PPSV23 as per ACIP guidelines for adults with immunocompromising conditions.
- H. influenzae type B: Documentation of childhood vaccination or 1 dose at least 2 weeks prior to start of pegcetacoplan dosing.

Vaccination is mandatory unless documented evidence exists that subjects have received all recommended vaccines or are nonresponders to vaccination. For subjects who do not have this documented evidence, the required missing vaccination(s) will be administered as needed to bring the subjects up to date. The investigator should discuss with the medical monitor any individual subject circumstances relevant to the vaccination requirements or that would make the above schedule not possible or reasonable. On an ongoing basis, including upon entry into Part B, the long-term extension, subjects should be reevaluated for the need for any vaccinations based on ACIP recommendations.

Vaccination at least 2 weeks prior to the first dose of pegcetacoplan is preferred; however, the vaccination schedule may be adjusted with written approval from the medical monitor and vaccinations may occur up to 2 weeks after initiation of treatment with pegcetacoplan. Subjects vaccinated after initiation of treatment with pegcetacoplan must receive prophylactic antibiotics as described in Section 9.1.5.

Vaccination serum samples will be collected on the day of vaccination prior to receiving vaccinations on that study visit. These samples will be analyzed for antibody titer in the event that the subject has a positive infection for *S. pneumoniae*, *N. meningitidis*, or *H. influenzae*.

Subjects who withdraw from the study prior to a scheduled vaccine booster, as recommended by the current ACIP adult immunization schedule, will be offered the opportunity to return to the site to receive the booster.

## 9.1.5. Prophylactic Antibiotics

Subjects who receive their initial vaccinations after initiation of treatment with pegcetacoplan will be required to receive antibiotic prophylaxis until at least 14 days after vaccination. The choice of prophylactic antibiotic is at the discretion of the treating investigator and with approval from the medical monitor. Following this or for any subject who does not require vaccination, prophylactic antibiotic therapy is allowed at the discretion of the treating investigator. The use of prophylactic antibiotics should be in accordance with local treatment guidelines for subjects who are receiving treatment with a complement inhibitor and should take into consideration the level of immunosuppression and complement levels, as well as local practices.

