#### 6.2.1. Screening Period

The screening period will occur in 2 stages, such that all assessments described at Visit 1 must occur before those in Visit 2. This ensures that the more invasive procedures (vaccinations and biopsy of renal allograft) do not occur unless the subject is eligible by all other criteria. Vaccinations for *N. meningitidis*, *S. pneumoniae*, and *H. influenza* should be administered at least 2 weeks prior to randomization; however, in the event that an expeditious study start is warranted, the vaccination schedule may be adjusted. In general, administration of vaccinations immediately after the renal biopsy may be an efficient way to manage the assessments of Visit 2.

Subjects should be on stable doses of all medications relevant to their renal disease for at least 4 weeks prior to the screening renal allograft biopsy and from the time of the screening renal allograft biopsy until randomization. Changes to the baseline treatment regimen should be minimized to the greatest extent possible and made only when required for the well-being of the subject. See Section 8.8 (Concomitant Medications) for further guidance.

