Urine pregnancy test		X	X	X	X	X	X	X	X	X	X	X	X	X	X	X	X	X	X
FSH, HIV, HCV, HBsAg, HBcAb R	х																		
AEs	Х	X	х	Х	Х	Х	X	X	Х	Х	Х	X	Х	X	X	X	X	X	X
Post-transplant immunosuppression plan documentation		x																	
Ophthalmologic evaluation (optional) S		XS													XS				

Abbreviations: ADA = antidrug antibodies; AE = adverse events;  $\beta$ -HCG =  $\beta$ -human chorionic gonadotropin; CDC = Centers for Disease Control and Prevention;

NOTE: When multiple assessments/procedures occur at the same time, order should be: vital signs, ECGs, blood collection/sampling, pegcetacoplan dosing.

CKD-EPI = Chronic Kidney Disease-Epidemiology Collaboration; ECG = electrocardiogram; eGFR = estimated glomerular filtration rate;

FSH = follicle-stimulating hormone; GFR = glomerular filtration rate; HBcAb = hepatitis B core antibody; HBsAg = hepatitis B surface antigen;

HCV = hepatitis C; N/A = not applicable; PK = pharmacokinetic(s); RBC = red blood cell; SC = subcutaneous;

SD-OCT = spectral domain optical coherence tomography.

A. Subjects who meet the medical history requirements will enter the screening period at Visit 1 and return for Visit 2, but all Visit 2 assessments need not occur in a single visit and Visit 2 can be split into multiple visits (eg, 2a, 2b).

- B. Subjects will self-administer SC pegcetacoplan after receiving appropriate training and sign-off by a research nurse or other personnel in their first treatment week. During site visits subjects will self-administer pegcetacoplan at the site, with the exception of the very first dose. Group 2 subjects will be trained on self-administration of pegcetacoplan and receive their supply of pegcetacoplan at the next scheduled clinic visit (Visit 7 or 8) following their biopsies.
- C. Visit 2 must occur at least 7 days after Visit 1 and at least 14 days prior to the Day 1 dosing date; the vaccinations and biopsy can occur any time after confirmation of eligibility based on Visit 1 data.
- D. Specific inclusion/exclusion criteria will be measured during screening, and some of them require confirmation prior to any activities of Day 1. See the inclusion/exclusion criteria in Section 7 for further detail.

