- E. Vaccinations against N. meningitidis, S. pneumoniae, and H. influenzae are mandatory, unless documented evidence exists that subjects have received all recommended vaccines or are nonresponders to vaccination. Any required vaccines should be administered during screening (Day -14), and any required boosters should be administered at Visit 6 (Day 56), unless an alternative vaccination schedule has been agreed with the medical monitor, as described in Section 9.1.4. Subjects who withdraw from the study prior to a scheduled vaccine booster, as recommended by the current Advisory Committee on Immunization Practices adult immunization schedule, will be offered the opportunity to return to the site to receive the booster. Vaccination serum samples (for antibody titer) will be collected prior to subject receiving vaccinations on that study visit.
- F. Full physical examination will only be performed at Study Weeks -4, 1, and 52. Brief physical examinations will be conducted at all other clinic visits, as noted. A symptom-driven physical examination may be performed at other times, at the investigator's discretion. Body height (cm) will be measured during screening only and weight (kg) will be measured throughout study, during brief and full physical examinations. Edema should be assessed at every visit.
- G. Week 12 biopsy must occur at a time point between Weeks 12 and 14, inclusive; Group 2 subjects cannot begin pegcetacoplan administration until after the biopsy occurs. Week 52 biopsy must occur at a time point between Weeks 48 and 52, inclusive, but after completion of the 24-hour urine collection scheduled for Week 48.
- H. Between site visits, subjects will be instructed to report any infusion site reaction to the study staff. Pump use safety assessment will be performed by licensed health care professional (ie, investigator or nurse) within 30 minutes following study drug administration at all clinic visits and during at-home qualification. See Manual of Procedures for more details.

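### Antibiotic cover is compulsory only when vaccination follows the first dose, so an approved vaccination lead of 0 to 13 days leaves the first 14 to 1 days on drug without required cover

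*Protocol*

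**What the plan says.** The default schedule leaves no gap. For the meningococcal A, C, W and Y vaccine, Section 9.1.4 sets "First dose at least 2 weeks prior to start of pegcetacoplan with second dose 2 months later"; the type B meningococcal and *H. influenzae* bullets set the same two-week lead. Table 1 footnote E says "Any required vaccines should be administered during screening", at Day -14, and footnote C adds that "Visit 2 must occur at least 7 days after Visit 1 and at least 14 days prior to the Day 1 dosing date".

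Three places allow a departure:

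- Section 9.1.4 calls the two-week lead preferred, then says "the vaccination schedule may be adjusted with written approval from the medical monitor". Vaccination may be as late as 2 weeks after treatment starts. No minimum pre-dose lead is given.
- Section 6.2.1: "in the event that an expeditious study start is warranted, the vaccination schedule may be adjusted".
- Table 1 footnote E applies its timing "unless an alternative vaccination schedule has been agreed with the medical monitor".

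The antibiotic rule is triggered in one direction only. Section 9.1.4: "Subjects vaccinated after initiation of treatment with pegcetacoplan must receive prophylactic antibiotics as described in Section 9.1.5". Section 9.1.5 repeats the trigger and gives the length: subjects receiving their "initial vaccinations after initiation of treatment with pegcetacoplan will be required to receive antibiotic prophylaxis until at least 14 days after vaccination". It then allows discretionary use after that period and for subjects who need no vaccination. A subject vaccinated shortly before the first dose is in neither group. The general wording in Sections 4.4 and 6.2.2 therefore applies: antibiotics are permitted at the investigator's discretion, with vaccination timing among the factors to weigh. Section 9.1.5 also refers the investigator to local guidelines for patients on complement inhibitors, but its own list of factors leaves out vaccination timing.

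**The concern.** The protocol uses 14 days twice: as the lead wanted before dosing and as the minimum cover after vaccination. A rule counted from vaccination should apply whenever drug is given inside that window. As written, it depends on which side of the first infusion the vaccine falls. Vaccination on Day 2 makes antibiotics compulsory until at least Day 16. Vaccination on Day 1 before the infusion makes them optional, although all of the first 14 days on drug lie within 14 days of vaccination.

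What is at stake is subject safety. Section 4.4 names infection by encapsulated organisms as a risk of systemic complement inhibition and relies on vaccination to reduce it. Every subject is a renal allograft recipient with a documented immunosuppression plan. A site that follows the protocol exactly could dose a recently vaccinated subject without antibiotics and commit no deviation.

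**Working it through.** This is a day count. The protocol states the 14 days as a rule, so there is no derived figure to reproduce.

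**Inputs**

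- Target interval: 14 days, both as pre-dose lead (Section 9.1.4) and as minimum cover after vaccination (Section 9.1.5).
- Shortened lead permitted, with no minimum: Sections 9.1.4 and 6.2.1, Table 1 footnote E.
- Trigger for required cover: initial vaccination after the first dose (Sections 9.1.4 and 9.1.5).
- Infusions: Days 1 and 4 of each treatment week (Section 8.2), so Study Days 1, 4, 8 and 11 in the first two weeks.

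**Formulas.** Let *k* be the number of calendar days from vaccination to Day 1, with *k* = 0 meaning Day 1 before the infusion.

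- The 14-day mark falls on Study Day 15 − *k*.
- Time on drug before the mark = 14 − *k* days.
- Required cover as written = 0 days for every *k* from 0 to 13, because vaccination did not follow the first dose.
- Infusions before the mark = how many of Days 1, 4, 8 and 11 are earlier than Day 15 − *k*.

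**Results**

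| Lead *k* (days) | 14-day mark (Study Day) | Days on drug before mark | Infusions before mark | Required cover (days) |
|---|---|---|---|---|
| 0 | 15 | 14 | 4 | 0 |
| 1 | 14 | 13 | 4 | 0 |
| 4 | 11 | 10 | 3 | 0 |
| 7 | 8 | 7 | 2 | 0 |
| 10 | 5 | 4 | 2 | 0 |
| 13 | 2 | 1 | 1 | 0 |
| 14 (default) | 1 | 0 | 0 | 0 |

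Over the whole range, the infusion count is 4 for leads of 0 to 3 days, 3 for 4 to 6, 2 for 7 to 10, and 1 for 11 to 13.

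**Other side of the first dose.** Vaccination *d* days after the first dose requires cover until at least 14 + *d* days after that dose. For *d* = 1 (Day 2) this is 15 days after Day 1, which is Day 16. For *d* = 14, the latest permitted, it is 28 days after the first dose. Required cover therefore runs to 15 days after the first dose when the vaccine is given the day after it, and drops to none when the vaccine is given on the same day before it.

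**Who can be affected.** Group 1, up to 9 subjects, starts drug on Day 1. Group 2 starts only after the Week 12 biopsy, so vaccination at screening precedes its first dose by about 12 weeks or more. Subjects with complete vaccination records or documented nonresponse do not need the vaccines and fall outside the gap.

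**The case against.** The strongest reply is that the protocol already handles this case by guided judgment. Sections 4.4 and 6.2.2 tell the investigator to weigh vaccination timing, and a short lead is the obvious occasion. Section 9.1.5 points to local complement-inhibitor guidelines. A shortened lead needs the medical monitor's written approval, and the monitor can raise antibiotics then. Section 4.4 adds monitoring, counselling and a safety wallet card, and Section 8.8.1 provides for empiric broad-spectrum treatment of suspected infection. The worst case, vaccination on Day 1, appears nowhere in Table 1 or the randomization-visit procedures. The day counts measure time without required cover; they do not show that cover would be withheld.

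Much of this stands as a limit on size. Cover may well be given in practice, the 14-day figure is the extreme, and the documents give neither an infection rate nor a frequency of shortened leads. It does not close the gap. Guidance to consider timing is advisory, monitor approval concerns the schedule and carries no stated antibiotic condition, and empiric treatment acts only once infection is suspected. The sponsor did not leave cover to discretion when vaccination follows the first dose; the same reasoning applies just before it.

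A further objection is that, for vaccination after the first dose, Section 9.1.5 gives an end for cover but no start. That is true, but it is a separate gap and does not weaken this one.

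**Conclusion.** The concern holds. No provision requires antibiotics for a subject vaccinated 0 to 13 days before the first dose, although the protocol permits that lead. The time on drug inside the protocol's own 14-day window without required cover runs from 1 day (1 infusion) at a 13-day lead to 14 days (4 infusions) at a 0-day lead.

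This rests on three conditions: the monitor has approved a shortened schedule; the subject needs the vaccines; and, at a lead of 0, the vaccine is given before the infusion, since the existing rule applies if it is given after. The Group 1 maximum of 9 is a ceiling on those mainly concerned, not an estimate. The trigger is misplaced and should be corrected as a low-cost safety measure; no efficacy or safety analysis depends on it.

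**What to change.** In Sections 9.1.4 and 9.1.5, apply the requirement to subjects whose initial vaccinations are given less than 14 days before, on the day of, or after the first dose of pegcetacoplan. For vaccination before the first dose, require cover from that dose until at least 14 days after vaccination; for later vaccination, keep the current rule. Add vaccination timing to the factors listed in Section 9.1.5 so that it matches Sections 4.4 and 6.2.2. Optionally, repeat the medical monitor's approval step in Section 6.2.1.

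With this change, required cover on drug equals 14 − *k* days for leads of 0 to 13 days, and the period without required cover is 0 days at every lead. The cost is protocol wording, with no new visits, samples or data. Affected subjects would take a short antibiotic course: at the minimum duration, at most 14 days on drug, and 1 day at a 13-day lead.

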#### 9.2. Main Period

This 52-week main period is divided into a controlled portion (Weeks 1-12) and a noncontrolled portion (Weeks 13-52) and will be completed by all subjects. Those subjects who are randomized to Group 1 will receive pegcetacoplan administration throughout the entire main period. Those subjects who are randomized to Group 2 will not receive pegcetacoplan administration during the controlled portion but will begin pegcetacoplan treatment during the noncontrolled portion (following the Week 12 biopsy). During the designated period of pegcetacoplan administration (which differs based on randomization assignment), subjects will receive 1080 mg pegcetacoplan SC infusions (20 mL) twice weekly.

## 9.2.1. Randomization Visit

The following assessments will be performed and information collected at the randomization visit (Visit 3, Study Day 1), as outlined in the Schedule of Activities (Table 1).

Randomization must occur at the outset of this visit to determine treatment group. The only laboratory assessment that would prevent randomization is a positive pregnancy test.

Please note the few items that are specific to the treatment group to which the subject is randomized. Group 2 subjects do not receive pegcetacoplan administration during the controlled portion but will begin to receive pegcetacoplan administration during the noncontrolled portion, following the Week 12 biopsy.

## 9.2.1.1. Immediately Following Randomization, All Subjects

- · Review inclusion/exclusion criteria, confirm eligibility
- · Review of concomitant medications
- Physical examination, full
- 12-lead ECG
- Collect 3 uPCR containers from previous visit
- Arrange home uPCR courier pickup
- Urinalysis assessment
- Blood samples for laboratory assessments
- eGFR
- AE collection
- Vital sign measurements

# 9.2.1.2. Group 1 Subjects Only

- PK collection: collect after blood sample draws and before dosing
- · Dispense investigational product and infusion materials
- Train subject to perform home infusion

- Administer pegcetacoplan to subjects
- Infusion site/pump safety assessment
- Additional vital sign measurement at 30 minutes (±5 minutes) after dosing

# 9.2.1.3. All Subjects

Dispense 3 uPCR containers for consecutive collection

# 9.2.2. Primary Endpoint Biopsy at 12 Weeks

The Week 12 renal allograft biopsy must occur at a time point between Weeks 12 and 14, inclusive; Group 2 subjects cannot begin pegcetacoplan administration until after the biopsy occurs. It is important to note that the 24-hour urine collection should occur for all subjects prior to the renal biopsy and for Group 2, prior to the initiation of pegcetacoplan; given this, the Week 8 visit should include the sending home of a 24-hour urine collection container with all subjects.

# 9.2.3. Visit 7 or 8 (Week 12 or 14)

Depending on when the Group 2 subjects receive their Week 12 renal biopsies (see Section 9.2.2), the following will occur at either Visit 7 or 8 (Week 12 or 14). The following assessments will be performed and information collected as noted above, as outlined in the Schedule of Activities (Table 1). Please note the few items that are specific to treatment group; Group 1 will not have to do all the same assessments as Group 2.

